6 REGULATORY ASPECTS AND SAFETY

6.1 Local regulations / Declaration of Helsinki

This study is conducted in compliance with the protocol, the current version of the Declaration of Helsinki, the ICH-GCP, the HRA as well as other locally relevant legal and regulatory requirements.

6.2 (Serious) Adverse Events and notification of safety and protective measures

A **Serious Adverse Event (SAE)** (ClinO, Art. 63) is any untoward medical occurrence that

- Results in death or is life-threatening,
- Requires in-patient hospitalisation or prolongation of existing hospitalisation,
- Results in persistent or significant disability or incapacity, or
- Causes a congenital anomaly or birth defect

Both Investigator and Sponsor-Investigator make a causality assessment of the event to the trial intervention, (see table below based on the terms given in ICH E2A guidelines). Any event assessed as possibly, probably or definitely related is classified as related to the trial intervention.

Relationship	Description
Definitely	Temporal relationship Improvement after dechallenge* Recurrence after rechallenge (or other proof of drug cause)
Probably	Temporal relationship Improvement after dechallenge No other cause evident
Possibly	Temporal relationship Other cause possible
Unlikely	Any assessable reaction that does not fulfil the above conditions
Not related	Causal relationship can be ruled out
*Improvement after dechallenge only taken into consideration, if applicable to reaction	

Both Investigator and Sponsor-Investigator make a severity assessment of the event as mild, moderate or severe. Mild means the complication is tolerable, moderate means it interferes with daily activities and severe means it renders daily activities impossible.

Reporting of SAEs (see ClinO, Art. 63)

All SAEs are documented and reported immediately (within a maximum of 24 hours) to the Sponsor-Investigator of the study.

If it cannot be excluded that the SAE occurring in Switzerland is attributable to the intervention under investigation, the Investigator reports it to the Ethics Committee via BASEC within 15 days.

If the SAE occurs at one of the study sites, the coordinating Investigator reports the events to the Ethics Committee concerned, within 15 days.

Exemptions from expedited reporting may be possible if the SAE is either a clear result of the underlying disease or well-known. These are defined below:

- Death
- Haemorrhagic transformation to an ischemic stroke
- Recurrent ICH
- Epileptic seizure
- Infection of any kind (i.e. surgical site infection, pneumonia, UTI etc.)
- Persistent focal neurological impairment

Follow up of (Serious) Adverse Events

These patients will be followed according to the normal procedures of follow up in case of (S)AE

within our clinic. These patients are followed periodically in an ambulatory setting until the (S)AE stabilizes or resolves.

Notification of safety and protective measures (see ClinO, Art 62, b)

If immediate safety and protective measures have to be taken during the conduct of the study, the investigator notifies the Ethics committee of these measures, and of the circumstances necessitating them, within 7 days.

6.3 (Periodic) safety reporting

An annual safety report (ASR/DSUR) is submitted once a year to the local Ethics Committee by the Investigator (ClinO, Art. 43 Abs).

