7.2 Risk-benefit assessment

This study aims to prove the superiority of ES and BMT compared to BMT alone for a devastating disease with currently insufficient effective treatment. However, potential risk and SAEs can be anticipated.

This study carries relevant risk of death and disability for the included patients due to the underlying disease of SSICH, however if left untreated, outcome may be even worse with a 30-day mortality up to 45% reaching to 54% at one year. The mortality rates however can be attributed almost exclusively to the underlying disease rather than the procedure. Since this is a surgical procedure, risks like bleeding, wound infections, surgical site infection, and complications related to anaesthesiologic procedures may occur. Furthermore, the procedure might, in extremely rare cases, lead to the death of the participant. Also, due to the location of SSICH, important brain structures have to be passed to access the hematoma cavity and, despite all efforts to conserve them, might be damaged.

When compared to the potential damage inflicted by untreated SSICH however, these complications are acceptable. If our hypothesis is correct, then the participants might benefit in form of better survival and functional outcome rates from the proposed intervention.

To minimise the risk of complications, two of the senior neurosurgeons at our institution, one of them being the chief of cerebrovascular neurosurgery, have prepared a standardised surgical procedure which will be taught to all involved surgeons via proctor workshop training. The surgical procedure itself will be carried out adhering to the highest neurosurgical standards. Careful preoperative planning with BrainLab® neuronavigation (or an equivalent neuronavigation system), the minimally invasive nature of the proposed surgical method, the shorter duration of surgery, a more complete hematoma evacuation under full sight and irrigation of active bleeding sites will contribute to reducing the risk of possible AEs for the participants.

Furthermore, participants will receive the medical standard of care before and after the surgical intervention as well as in the control group and are closely monitored during their stay at our institute.

If our hypothesis proves to be true, then surgical evacuation for SSICH may ameliorating mortality and functional outcome for future patients suffering from this devastating disease.

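### The exemption list in section 6.2 has no causality condition, so an SAE possibly related to the surgery could be left out of the 15-day Ethics Committee report

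*Protocol*

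**What the plan says.** All of the reporting rules are in protocol section 6.2.

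- **Causality threshold:** "Any event assessed as possibly, probably or definitely related is classified as related to the trial intervention".
- **Expedited rule**, with a 15-day limit and the Ethics Committee as recipient: "If it cannot be excluded that the SAE occurring in Switzerland is attributable to the intervention under investigation, the Investigator reports it".
- **Exemption:** "Exemptions from expedited reporting may be possible if the SAE is either a clear result of the underlying disease or well-known". The protocol says that the exempt events are defined in the list that follows. The list has six items: death, haemorrhagic transformation to an ischaemic stroke, "Recurrent ICH", epileptic seizure, "Infection of any kind (i.e. surgical site infection, pneumonia, UTI etc" and so on, and persistent focal neurological impairment.

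No item is qualified by causality, arm or timing.

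Section 7.2 describes what the operation itself may cause: "risks like bleeding, wound infections, surgical site infection, and complications related to anaesthesiologic procedures may occur". It adds death from the procedure, in extremely rare cases, and damage to brain structures on the access path. Section 3.2 counts surgical site infection in the intervention group only.

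**The concern.** An exemption for events expected from the haemorrhage is reasonable: deaths and persisting deficits will be common in both arms, and reporting each one individually would add little. But this exemption has two alternative grounds, and the second, that the event is well-known, does not require the disease to be the cause. A recognised complication of the operation satisfies it. The list then works by type of event, so the same event can be reportable under the causality rule and exempt under the list.

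What is at stake is timely outside scrutiny of harms particular to the experimental arm, in an open-label surgical trial that enrols patients unable to consent. The Ethics Committee would receive such a case routinely only in the annual safety report (section 6.3), up to about 12 months later instead of within 15 days, while randomisation continues.

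**Working it through.** No sample size or error rate is involved. The check sets the rules and lists side by side.

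**Step 1: surgical risks in section 7.2 against the exempt list in section 6.2.**

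| Risk named in 7.2 | Matching item in 6.2 | On the list? |
|---|---|---|
| Bleeding | Recurrent ICH | When intracerebral |
| Wound infection | Infection of any kind | Yes |
| Surgical site infection | Named under infection | Yes |
| Anaesthetic complications | None | No, unless an infection such as pneumonia |
| Death from the procedure | Death | Yes |
| Damage to brain structures | Persistent focal impairment | When the deficit persists |

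Three risks are fully covered, two are covered under a condition and one is not covered: 3 + 2 = 5 of 6. If wound and surgical site infection are counted as one group, the result is 4 of 5. The count depends on the grouping, but either way only anaesthetic complications stay outside.

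**Step 2: does the list reach harm that the disease cannot cause?** Surgical site infection arises only where there is a surgical site, as section 3.2 recognises. It cannot be a clear result of the haemorrhage, so it can be on the list only through the well-known alternative. The list is therefore not confined to disease events.

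**Step 3: one event under both rules.** Take a serious rebleed after evacuation.

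- It follows the operation in time, and the underlying disease is another possible cause. By the causality table in 6.2 this is *possibly* related.
- *Possibly* counts as related, and attribution cannot be excluded, so a 15-day report is due.
- Recurrent ICH is on the list, so an exemption may be possible.
- No sentence says whether a related event can still be exempt.

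**Step 4: what remains if the exemption is used.**

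| Channel | Where | Limit |
|---|---|---|
| 24-hour report, all SAEs | 6.2 | To the Sponsor-Investigator only |
| Annual safety report | 6.3 | Reaches the Ethics Committee once a year |
| Notice of protective measures, 7 days | 6.2 | Only once a measure has to be taken |
| Notice of premature termination or interruption, 15 days | 6.7 | Only once the study is stopped or interrupted |
| Independent DSMB | 9, Appendix 2 | No route or timing for individual SAEs is described |

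Only the annual report brings an individual exempted event to the Ethics Committee as routine.

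**The case against.** The best defence is that the exemption is permissive. It says that exemptions may be possible, so nobody is obliged to withhold a report, and a careful investigator would hardly call an intra-operative bleed a clear result of the disease. On this view the protocol has a rule and an exception whose order is merely unstated. That stands as a limit on the claim: a reader might infer that a fatal bleed during surgery would go unreported, and the text does not support this. It supports only that such an event could be treated as exempt. The gap stays, because the well-known alternative and the naming of surgical site infection let the exception reach procedure-related events.

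A second defence is that oversight does not rest on the 15-day report alone. This also stands. All SAEs reach the Sponsor-Investigator within 24 hours, an independent DSMB exists, and mortality, recurrent SSICH, seizures and infections are secondary outcomes in section 3.2. A reader might infer that these harms are lost to oversight, or that the annual report is the only path to the Ethics Committee. Neither is so. What can be lost is expedited reporting of the individual case.

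Third, persistent focal impairment may be meant as persistence of the presenting deficit, since section 4.1 requires a focal deficit or reduced consciousness at entry. That is a natural reading, but the wording does not exclude a deficit caused by the access path.

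Finally, the causality table is worded for drugs, for example "Recurrence after rechallenge (or other proof of drug cause", and a reader might conclude that it misclassifies surgical events. This has no effect on reporting: *possibly* already counts as related, so failing to reach *probably* or *definitely* changes nothing.

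**Conclusion.** The point holds as a conflict of rules within section 6.2. For a listed event at least possibly related to surgery, one rule requires a 15-day report, another permits exemption, and neither is given precedence. The reach is wide, at five of the six surgical risks named in section 7.2, two of them conditionally. The consequence is limited to expedited reporting to the Ethics Committee, where 15 days could become up to about 12 months.

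This assumes that the list is read as written, without an unstated causality condition, and that the investigator chooses to use the exemption. Whether the cited ordinance allows such exemptions cannot be judged from the protocol. Nor can the number of affected cases be estimated: the planned outcome rates include disabled survivors, and the mortality quoted is for untreated haemorrhage, so neither measures deaths caused by the procedure.

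The wording should be corrected because it concerns participant protection. It does not affect the endpoint, the randomisation or the analysis, so it is a should-fix and not a fatal defect.

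**What to change.** Add one sentence to section 6.2: *Listed events are exempt from expedited reporting only if both the Investigator and the Sponsor-Investigator rate them unlikely or not related to the trial intervention.* Section 6.2 already has both of them assess causality, so no new assessment is needed, and any disagreement leads to a report.

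Delete surgical site infection from the infection item, and delete the well-known alternative from the exemption. Removing the name alone would not be enough, because infection of any kind would still include it. The causality sentence does the main work.

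The cost is a wording amendment to section 6.2 and some additional 15-day reports, mainly from the intervention arm. No extra patients, visits or procedures are needed, and the causality scale can stay as it is.

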6.4 Radiation

There will be no additional radiation for this study other than the planned cCT-scans, which are in accordance with routine clinical practice for SSICH. Every one of these cCT-scans will have an approximate radiation dose of 4.5 mSv. If the permitted dose guidance value (5 mSv per year if no direct benefit is expected for the participants) is exceeded at any time, the local Investigator notifies the Ethics Committee via BASEC within 7 working days of it becoming known (see ClinO, Art. 44).

6.5 Pregnancy

We plan to assess pregnancy or a possible pregnancy in women of childbearing age before inclusion. If the patient's history is positive for a pregnancy or a possible pregnancy, the patient will be excluded. If a participant gets pregnant during the study, they will receive an MRI instead of a CT scan and can continue with the study procedures. In case of pregnancy during the course of the study, the Sponsor-Investigator will be notified within a maximum of 24 hours and the outcome of the pregnancy will be followed up. The patient will be informed, that she has to contact the study team in case of pregnancy and after birth.

6.6 Amendments

Substantial changes to the study setup and study organization, the protocol and relevant study documents are submitted to the Ethics Committee for approval before implementation. Under emergency circumstances, deviations from the protocol to protect the rights, safety and well-being of human subjects may proceed without prior approval of the Ethics Committee. Such deviations shall be documented and reported to the Ethics Committee as soon as possible.

Substantial amendments are changes that affect the safety, health, rights and obligations of participants, changes in the protocol that affect study objective(s) or central research topic, changes of study site(s) or of study leader and sponsor (ClinO, Art. 29).

A list of all non-substantial amendments will be submitted once a year to the competent EC together with the ASR.

6.7 (Premature) termination of study

The Sponsor-Investigator may terminate the study prematurely according to the following circumstances:

- Arising ethical concerns
- Insufficient participant recruitment
- When the safety of the participants is doubtful or at risk (e.g. when the benefit-risk assessment is no longer positive)

- If alterations in accepted clinical practice that make the continuation of the study unwise arise
- Presence of early evidence of harm or benefit of the experimental intervention

Upon regular study termination, the Ethics Committee is notified via BASEC within 90 days (ClinO, Art. 38).

Upon premature study termination or study interruption, the Ethics Committee is notified via BASEC within 15 days (ClinO, Art. 38).

Biological materials collected until premature termination of the study will be evaluated according to the study protocol as will all acquired data to this point. The study will be published with the data collected until the point of premature termination while mentioning in the publication that a premature termination according to whatever reasons applied was chosen.

6.8 Insurance

Insurance for this study will be supplied by Helvetia Schweizerische Versicherungen AG. A contract was issued between the Helvetia Schweizerische Versicherungs AG and the Sponsor [name]. med. [name].

7 FURTHER ASPECTS

7.1 Overall ethical considerations

SSICH is a devastating cerebrovascular disease with currently insufficiently available effective treatment options. Our proposed approach of endoscopic evacuation of SSICH is based on pathophysiological and clinical evidence on the importance of early reduction in hematoma volume, as well as lessons learned from previous surgical trials. It is vital to evaluate new surgical methods to ameliorate patient's survival rate and to lower the social burden for the respective families. Conventional craniotomy has failed to show a significant impact on the functional outcome and mortality rates, minimally invasive surgical techniques however showed promising results. Especially ES has proven to inflict less damage to the surrounding brain tissue compared to the open surgical approaches due to its minimally invasive nature. Therefore, we plan to assess this surgical method in comparison to the current gold standard of treatment for SSICH (BMT) in a randomised controlled fashion to generate valid data on the best treatment modality for SSICH. Both are accepted treatment options for SSICH.

If ES fails to show significant effects on the specified outcome measures in the planned "interim analysis", the study will be prematurely terminated and BMT for ICH will be applied immediately for all patients.

All patients have the right to voluntarily participate in this study. Every participant, his legal guardian or his relatives have the right of information about the study and their study data.

Vulnerable populations may be included in this study as described in 4.2 "Recruitment, Screening and informed consent procedure". They might not be addressable at the time of inclusion, however, as soon as they are addressable again, they will be informed about the study according to the process in 4.2.

Overall, we consider this study to be fairly balanced between risk for the patients due to their initial condition compared to possible SAEs occurring through the surgical method proposed in this study.

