5.1.2.4 Stopping rule

The evidence is regularly calculated until either a pre-set level of evidence threshold, is achieved in favour of either of the hypotheses, or when the maximum sample size is reached. For the current study, we chose to set the maximum total sample size at 200, and the evidence threshold at a Bayes Factor of 10, which is generally considered as strong evidence. In the simulations below, however, we show the expected evidence up to 170 patients per arm.

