5.1.2.6 Conclusion of sample size estimation

Based on these results we assume that we will likely be able to stop collecting data before reaching **75 patients per arm (total of 150 patients) to reach a BF of 10**. We aim to collect a minimum of 40 patients per study arm. From that point on, we will perform the abovementioned BF test after every 40 new patients (about 20 per arm, exact number subject to randomization). The evidence is regularly calculated until either a pre-set level of evidence threshold is achieved in favor of either of the hypotheses (BF of 10 or 1/10 respectively, considered as strong evidence), or when the maximum sample size is reached. For the current study, we chose to set the maximum total sample size at 200 (as deemed sufficient based on a frequentist sample size estimation for the same assumptions). If this threshold is not reached, a new cost-benefit analysis of continuing to collect data will be performed. However, as described above, this is highly unlikely. After data collection is deemed completed and follow-ups at 6 months are complete, all secondary and sensitivity analyses will be performed. For the data collected up to 40 per arm, a p-value may be calculated (sensitivity analysis) and used for a classical hypothesis test.

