5.1.3 Planned statistical methods

The primary analyses are performed following the intention-to-treat principle. Additionally, per-protocol analysis will be performed for sensitivity analysis. We study the ratio of positive outcomes in both study arms by performing a Bayesian A/B test after every 40 additional patients, using the method described by Gronau et al.[53]. Data collection (and the periodical analysis of these data) will continue until a Bayes Factor of 10 (or 1/10) is achieved. The odds

ratio and its 95% credible interval will be reported. Covariates ICH volume, presence of intraventricular bleeding, do-not-resuscitate orders, location of hematoma and centre will be included in a Bayesian logistic regression model

Secondary analysis is performed on the secondary outcomes. For continuous variables, a Bayesian regression with normal error term is used, for time-to-event outcomes Bayesian cox-regression is used, and for binary variables Bayesian logistic regression is used. Statistical analysis is performed with R version 4.2.1 or higher (R core Team, 2022)[54]. A complete mRS shift analysis will be calculated.

In parallel to the Bayesian primary analysis, we will perform a frequentist test of proportions comparing study arm for the first 100 patients per study arm. In the ES arm, a number of explorative analyses are performed, studying the relation between hematoma location, hematoma size, and treatment outcome. In particular, for parameters measured over time, figures are created illustrating the development over time at both the patient level and group level.

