5.1.4 Interim analysis

As described under “5.1.2.6. Conclusion of sample size estimation”, the data may be inspected any time, but we plan to perform the primary analyses after every 40 patients (20 per arm), and will stop data collection if the BF, in favor of either the null, or the alternative hypothesis is over 10.

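### Section 7.1 ends the trial when an interim look is not significant, whereas Section 5 says that an inconclusive look means continue

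*Protocol*

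**What the plan says.** **Section 7.1 (ethics).** The trigger is "If ES fails to show significant effects on the specified outcome measures in the planned" interim analysis. The consequence is mandatory: "the study will be prematurely terminated and BMT for ICH will be applied immediately for all patients". The section gives no threshold and does not say which of the repeated looks is meant. It refers to outcome measures in the plural.

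**Section 5 (statistics).** Section 5.1.4 says the investigators "will stop data collection if the BF, in favor of either the null, or the alternative hypothesis is over 10". Section 5.1.3 says "Data collection (and the periodical analysis of these data) will continue until a Bayes Factor of 10 (or 1/10) is achieved". Section 5.1.2.4 adds a ceiling: "For the current study, we chose to set the maximum total sample size at 200". Section 5.1.2.6 repeats that ceiling and says what follows it: "If this threshold is not reached, a new cost-benefit analysis of continuing to collect data will be performed".

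**Timing of looks.** Section 5.1.2.6 says "We aim to collect a minimum of 40 patients per study arm", then a test after every 40 new patients. Section 5.1.4 refers back to 5.1.2.6, but says that the data may be looked at whenever wished and that "we plan to perform the primary analyses after every 40 patients (20 per arm"). Section 5.1.3 and the statistical paragraph of the synopsis give the 40-patient interval without the maximum of 200.

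**The concern.** After a look that crosses no boundary, both rules cannot be obeyed: 7.1 ends the study and Section 5 continues it. Such looks are expected. Section 5.1.2.5 itself says that only half of simulated trials reach BF 10 by 40 per arm at the planned effect. Under 7.1, not yet having enough evidence is handled as if it were evidence of no benefit. The sequential design behind the sample size assumes the reverse. Whoever acts on an inconclusive interim result would find opposite instructions in the same protocol, and one of them could end a trial of a treatment that works as assumed.

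**Working it through.** **Inputs from the protocol.** Control rate 0.50 (5.1.2.1). Risk ratio 1.6 (5.1.2.2), so the ES rate is 0.50 × 1.6 = 0.80. Allocation 1:1, two-sided hypothesis, BF threshold 10, maximum 200. Looks are read from 5.1.2.6 as 40, 60, 80 and 100 per arm.

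**Assumptions.** Section 5.1.2.3 names only the package's default priors, without values. I take N(0,1) on the log odds ratio ψ and N(0,1) on the mean log odds β. Alpha is taken as 0.05 two-sided, since none is stated. The second scenario, an ES rate of 66.7%, is mine: odds ratio 2, risk ratio 0.667/0.50 = 1.33, inside the simulated range of 1.2 to 1.6.

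**Bayes factor.** Under H1, logit p(BMT) = β − ψ/2 and logit p(ES) = β + ψ/2; under H0, ψ = 0. BF10 is the marginal likelihood under H1 divided by that under H0, by Gauss-Hermite integration. Single-look probabilities sum both binomial distributions exactly; sequential ones come from 20,000 simulated trials.

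**Step 1. The protocol's own figures.**
- At 70 per arm it states about 90%. I get 85.7% for a single look and 88.3% to 90.5% when monitored every 10 patients per arm down to every patient, so this is reproduced.
- At 40 per arm it states 50%. I get 55.0% for a single look and 58% to 63% with monitoring, which is somewhat higher. I therefore also carry the protocol's 50%.

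**Step 2. Chance that 7.1 ends the trial at 40 per arm.**

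*Significant means BF10 of at least 10 in favour of ES.*
- 50% vs 80%: 1 − 0.550 = 45.0% (1 − 0.50 = 50% on the protocol's figure).
- 50% vs 66.7%: 1 − 0.108 = 89.2%.

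*Significant means two-sided p<0.05.* Power = Φ{[d − 1.96√(2p̄(1−p̄)/n)] / √([p₁(1−p₁)+p₂(1−p₂)]/n)}.
- 50% vs 80%: Φ{(0.30 − 1.96 × 0.1067)/0.1012} = Φ(0.90) = 0.816, so 18% are ended. Exact enumeration gives 0.817.
- 50% vs 66.7%: Φ{(0.1667 − 1.96 × 0.1102)/0.1087} = Φ(−0.45) = 0.325. Exact enumeration gives 0.339, so 66% to 67% are ended.

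**Step 3. Cost in detection by 200 patients, BF reading.**

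| True rates | Section 5 rule alone | 7.1 applied at 40 per arm |
|---|---|---|
| 50% vs 80% | 97.1% | 55.0% |
| 50% vs 66.7% | about 42% | 10.8% |

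**Step 4. Can 7.1 be read as stopping when the BF favours the null?** The wording speaks of failing to show an effect, not of showing its absence. Under the assumed priors the smallest BF10 that any data can give is 0.41 at 40 per arm and 0.27 at 100 per arm. The 1/10 boundary is therefore out of reach within 200 patients, and on this reading 7.1 would never operate.

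**The case against.** The best defence is that 7.1 is one loose sentence in an ethics section, while the stopping rule is set out consistently in several statistical sections that a statistician would follow. That limits how likely the harm is, but it does not remove the contradiction: the 7.1 wording is mandatory and names the planned interim analysis.

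Several stronger readings are tempting, and the documents do not support them.

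- **That 7.1 would end half of trials at the planned effect and nine in ten at an odds ratio of 2, without qualification.** Those figures need significant to mean BF of at least 10, judged at 40 per arm. With p<0.05 they are about 18% and two thirds. The odds ratio of 2 is not a protocol assumption.
- **That most of the power is lost.** At the planned effect, on the BF reading, detection falls from 97% to 55%, a loss of under half. At an odds ratio of 2 most trials would not reach BF 10 by 200 even without 7.1 (about 42% do).
- **That the first look is at 20 per arm.** Section 5.1.4 refers back to 5.1.2.6 and its 40-per-arm minimum, and the 20 per arm is most naturally the increment. The wording is loose rather than a rival rule. The same goes for the missing maximum in 5.1.3 and the synopsis, which is an omission.
- **That 200 is a hard end.** Section 5.1.2.6 follows it with a cost-benefit analysis.
- **That the monitoring board would carry out 7.1.** Section 7.1 names no decision-maker, and 6.7 gives premature termination to the sponsor-investigator.
- **That a false conclusion of failure would be published.** Section 6.7 requires the publication to report an early termination and its reason.

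**Conclusion.** The contradiction stands and should be removed before any interim look is acted on. Section 7.1 terminates on a result that Section 5 treats as a reason to continue.

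Its size depends on what significant means, which the protocol does not say. Applied at 40 per arm, wrongful termination at the planned effect is about 18% (p<0.05) to 45% (BF of at least 10), or 50% from the protocol's own simulation. At an odds ratio of 2 it is about two thirds to 89%. The BF figures rest on assumed N(0,1) priors and the p-value figures on an assumed alpha of 0.05.

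That an inconclusive look is common at 40 per arm does not depend on these assumptions, since 5.1.2.5 says so. The loose look schedule and the missing maximum are secondary.

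**What to change.** 1. **Section 7.1:** replace the termination sentence with a reference to the rule in 5.1.2.6, so that a look crossing no boundary means continue to the next look.
2. **Sections 5.1.3, 5.1.4 and the synopsis:** state one look schedule (80, 120, 160 and 200 patients in total) and the maximum of 200, together with the cost-benefit clause that follows it. In 5.1.4, remove the wording that leaves the time of the first look open.
3. **Section 6.7:** leave unchanged. Termination by the sponsor-investigator, including for harm, does not depend on the 7.1 sentence.

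The cost is a few sentences of wording, with no change to sample size or data collection. Because a termination rule changes, Section 6.6 may class this as a substantial amendment needing Ethics Committee approval before implementation.
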